10.3 STUDY ASSESSMENTS AND PROCEDURES

Patients likely to fulfill the inclusion criteria and not meet any exclusion criteria will be provided with information on the study and invited to attend a subsequent screening visit. Only patients who have signed the informed consent form will participate in any study related procedures including blood testing and ECG.

At screening visit (Assessment 1) subjects will have a physical examination and an EDSS score rated. Blood samples will be taken for renal and liver function and a baseline ECG performed. Patients will complete a nine-hole peg test and a JTT. T25FW will be recorded and the patients invited to complete the MSIS-29, MSWS-12, DASH, AMSQ and SF-36 questionnaires. Patients with any abnormalities on ECG, blood tests will not be invited to a baseline visit and considered a screening failure.

Following screening visit subjects fulfilling the inclusion / exclusion criteria will have two baseline visits (Assessments 2 and 3) at the end of week one and end of week two. The 9-HPT, JTT and T25FW will be repeated to allow for training effects. Patients will be randomised to group A or group B and receive study medication or placebo at baseline visit based on their blinded randomisation (Assessment 3).

The first treatment period will be from the start of week 3 until the end of week 10. Patients will have an assessment at the end of week 6 (Assessment 4) and the end of week 10 (Assessment 5). At both assessments patients will have the 9-HPT, JTT, T25FW, MSIs-29, MSWS-12, DASH, AMSQ and SF-36 recorded. Weeks 11 and 12 will be a washout period (no drug/placebo). Assessment 6 will occur at the end of week 12 and will include recording of 9-HPT, JTT, T25FW, MSIs-29, MSWS-12, DASH, AMSQ and SF-36. Any adverse events will be recorded at each visit as will the use of concomitant medications.

The second treatment period will begin at the start of week thirteen with groups A and B switching study drug / placebo in a blinded manner. The second treatment period will continue for a further 8 weeks with two more assessments at week 16 (Assessment 7) and week 20 (Assessment 8). At both of these assessments subjects will complete the 9-HPT, JTT, T25FW, MSIs-29, MSWS-12, DASH, AMSQ and SF-36. At the end of week 20 and EDSS score will be recorded. Any adverse events will be recorded at each visit as will the use of concomitant medications.

There will be a final washout period (weeks 21 and 22) after which a final visit (assessment 9) will occur and subjects once again completing 9-HPT, JTT, T25FW, MSIs-29, MSWS-12, DASH, AMSQ and SF-36 and having an EDSS score recorded. Once again adverse events will be recorded.

(See Schedule of Events, page 15)

Figure 2: Schedule of events

Assessment	1 Screening Visit	2 Baseline Visit	3 Base - line Visit	4 Rx Phase 1	5 End of Rx Phase 1	6 End Wash- out phase	7 Rx Phase 2	8 End of Rx Phase 2	9 End of 2 week washout
Time (start/end week)	week 1 (start)	week 1 (end)	week 2 (end)	week 6 (end)	week 10 (end)	week 12 (end)	week 16 (end)	week 20 (end)	week 22 (end of trial)
Informed consent	X								
Serum pregnancy test (female subjects)	X								
EDSS	x							X	X
ECG	X								
Receiving Medication	No	No	Start drug	Continu e drug	Stop drug	Start drug	Continu e drug	Stop drug	Wash out
9- HPT	x	x	x	x	x	x	x	x	X
JTT	x	x	x	x	x	x	x	x	X
T25FW	x	x	x	x	x	x	x	x	X
MSIS-29	x		x	x	x	x	x	x	X
MSWS-12	x		x	x	x	x	x	x	X
DASH	x		x	x	x	x	x	x	X
AMSQ	x		x	x	x	x	x	x	x
SF-36	X		X	X	X	X	X	X	X
Adverse event recording				X	X	X	X	X	X
Concomitant medication recording	X		X	X	X	X	X	X	X
Study Drugs dispensed			X			X			

Description of Study Assessments

Medical and Surgical History will be recorded with particular attention on the diagnosis of MS, duration of MS and MS subtype.

Demographics

The date of birth, gender and race will be recorded.

Physical Examination

The complete physical examination will include the evaluation of the neurological system and a recording of the EDSS score and T25FW.

ECG Test

One ECG including a 12-lead examination will be performed at Screening (assessment 1).

Abnormal findings will be noted for clinical significance. The report will be signed by the investigator.

Clinical Laboratory Tests

1. Haematology: haemoglobin, WBC, RBC, platelet count
2. Biochemistry: creatinine or creatinine-clearance, sodium, potassium, liver function tests
3. All laboratory results will be reviewed and the reports signed by the investigator who will record in the CRF whether they are normal, abnormal but not clinically significant, or abnormal and clinically significant.

Pregnancy Tests

Serum pregnancy test and urine pregnancy test in women of childbearing potential will be performed.

Concomitant Medication

In addition to Fampyra, any other treatments or procedures that are considered necessary for the patient's welfare may be given at the discretion of the Investigator. Administration of continuous concomitant procedures and medications (including herbals and nutraceuticals) must be reported in the appropriate section of the CRF along with reasons for use. Continuous concomitant procedures and medications are defined as a treatment administered regularly for 2 weeks or more. The generic names for concomitant medications should be recorded, if possible. The total daily dose should be recorded in the CRF whenever possible. Concomitant use of medicinal products that are inhibitors of OCT2 for example, cimetidine will be noted and will be deemed exclusion criteria. Concomitant use medicinal products that are substrates of OCT2 for example, carvedilol, propranolol and metformin will also be noted and the investigator will decide if the subject should successfully complete screening.

10.3.1 Endpoints assessments

Endpoint assessment will include the 9-HPT; JTT and T25FW test

10.3.2 Efficacy Assessment

A responder to study medication will be a subject who has a 20% improvement in the 9-HPT at both on treatment visits (assessment 4 & 5 or 7 & 8) compared with baseline visits.

A secondary measure of upper limb responsiveness will be defined as a 20% improvement in from baseline in the average time taken to complete all seven tasks on the JTT “on treatment” (assessments 4 & 5 or 7 & 8) compared with baseline assessments (assessments 1,2 & 3).

A mobility responder to fampridine will be defined as a patient with both of the two “on treatment” T25FW assessments (assessments 4 & 5 or 7 & 8) being better than the maximum of any of the four “off treatment” assessments (assessments 1, 2, 3, & 9). Otherwise the patient will be deemed a non-responder.

The responders to the 9-HPT and/or JTT will be compared to the non-responders in relation to their changes in the DASH and AMSQ on treatment and off treatment at the baseline assessment. The change in the DASH and AMSQ in responders at Assessment 5 or 8 (week 10 or 20) will be compared to non-responders at that time-point.

Upper limb response will be examined at the end of treatment phase 1 and repeated at the end of the trial by comparing patients receiving active drug with those receiving placebo to assess any placebo effect and allow assessment of any residual beneficial effect on those who receive fampridine in treatment phase 1 and then switch to placebo in treatment phase 2. Response will again be considered as a 20% improvement in the 9HPT in the active treatment group compared with placebo and a 20% improvement from baseline in the time taken to complete all seven tasks in the JTT. See earlier comment

The responders to the T25FW will be compared to the non-responders in relation to their changes in the MSWS-12 on treatment and off treatment at the baseline assessment. The change in the MSWS-12 in responders at Assessment 5 or 8 (week 10 or 20) will be compared to non-responders at that time-point.

The patients’ scores on the MSIS-29 (physical) and SF-36 will be examined in relation to the objective changes (responder/non-responder) in the 9-HPT, JTT and the T25FW

Safety Assessment

Adverse events will be monitored, through out the study. Subjects will be required to inform the study team of all new or worsening symptoms within 24 hours of onset. All adverse events will be recorded in the CRF.

10.3.3 Method of assigning Subjects to treatment groups

Randomisation

Generation of Randomisation Codes

Subjects were randomised to each of two groups, A or B using the program:

<http://www.graphpad.com/quickcalcs/randomize1.cfm>

The randomisation sequence was generated on 07/03/2012.

Table 1. Randomisation Groups

Randomisation Groups	A = Initial treatment with Fampridine followed by placebo. B = Initial treatment with placebo followed by Fampridine.
----------------------	--

Security and Distribution of Randomisation Codes

The randomisation codes will be kept on the Pharmacy Network Drive in St. Vincent's University Hospital. A hardcopy will be kept in the Pharmacy Department in the clinical trial folder.

The investigators and subjects will not have access to the randomisation codes (double blind).

A copy of the randomisation code and individual product codes will also be kept in a sealed envelope, with signature and date across the seal, which may be opened by the Principal Investigator if an emergency code-break is required. This will be stored in a secure location in the Neurology department but can be accessed by the Principle investigator if needed.

Handling

Pharmacy staff will use the information when dispensing clinical trial medication to each subject to ensure the appropriate medication is dispensed (ie placebo or active).

Retention

The study pharmacist will retain the randomisation codes until the database is locked at the end of the trial. Thereafter, the randomisation code will be made known to the investigators.

Code-Break Mechanisms

In the case of emergency, when knowledge of the subject's study treatment assignment is essential for the clinical management of the subject. Any intentional or unintentional breaking of the blind will be recorded and reported to the sponsor as soon as possible.

After database is locked at the end of the trial.

Blinding

Procedure for blinding of Fampridine versus placebo.

1. Capsules look identical.

Fampridine and placebo capsules look identical.

2. Identical packaging

Fampridine and placebo are packaged in identical packaging.

3. Identical labeling

The label instructions will be identical for both. See copy of label below

Figure 3. Study drug label.

FAMPYRA® 10MG TABLETS OR PLACEBO						
Fampridine 10mg tablets or placebo						14 tablets
Take ONE tablet TWICE daily						
To be taken orally. For clinical trial use only.						Keep out of reach of children.
Patient	Name/ID	No.	_____			Store at room temperature in original container.
Date	_____					
Product	Code	No.	_____	Expiry	Date	

Principal Investigator: [name]. Trial Sponsor: SVUH						
Site: St. Vincent's University Hospital. Trial Ref. No. SVUHneur002						

4. Use of numbers in random order for product codes

Each product will be labeled with a product code. It was decided that 4-digit codes would be used.

Using Microsoft Excel, a sequence of 1400 numbers in numerical order was generated. The numbers range from 1,000 to 2,199. The numbers were then shuffled into random order for use as product codes.

The first 700 numbers in random order will be used as the Fampyra codes

The last 700 numbers in random order will be used as the placebo codes.

Use of numbers in random order for the product codes means that the investigators and subjects will not be able to determine from the product codes whether the patient is on active or placebo treatment. The codes will be used by the study pharmacist to ensure that patients are correctly dispensed active or placebo as required and to allow identification of active or placebo if unblinding required.

Who will be blinded?

The study will be conducted in a double-blind fashion. Study treatment assignment will be blinded for both the investigators and the subject.

The study pharmacist will retain the list of fampridine and placebo product codes.

Circumstances in which the blind would be broken

In the case of an emergency, when knowledge of the subject's study treatment assignment is essential for the clinical management of the subject, an investigator may unblind a subject. For example, the

blind would be broken in the event of a serious adverse effect experienced by a subject. Any intentional or unintentional breaking of the blind will be recorded and reported to the sponsor as soon as possible.

Procedure for unblinding

The Principal Investigator should be contacted if emergency unblinding is required. He will be provided with a sealed envelope (with signature and date across the seal) containing the Randomisation Code, active product codes and placebo product codes. The envelope may be opened if emergency unblinding is required.

This will be stored in a locked safe in the Neurology Department offices in St. Vincent's University Hospital.

The list of active and placebo product codes will be shuffled back into numerical order and saved as a separate file before being printed to allow quick identification of a particular product code if emergency unblinding is required.

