12.2.5 Emergency unblinding procedures

The principle investigator should be contacted if emergency unblinding is required. They will be provided with a sealed envelope (with a signature and date across the seal) containing the randomization code, active product codes and placebo product codes. The envelope may be opened if emergency unblinding is required.

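### The only written emergency code-break route is one envelope holding every code, so unblinding one subject can unblind the Principal Investigator to all

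*Combined protocol and SAP*

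**What the plan says.** Three places in the combined protocol and SAP describe the same device.

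- Section 10.3.3, Security and Distribution of Randomisation Codes: "A copy of the randomisation code and individual product codes will also be kept in a sealed envelope", which the Principal Investigator may open for an emergency code-break.
- Section 10.3.3, Procedure for unblinding: the Principal Investigator is given a sealed envelope "containing the Randomisation Code, active product codes and placebo product codes. The envelope may be opened if emergency unblinding is required".
- Section 12.2.5: again one envelope, "containing the randomization code, active product codes and placebo product codes".

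Two further remarks in section 10.3.3 foresee a look-up by product code. The pharmacist's codes serve "to allow identification of active or placebo if unblinding required", and both code lists are to be re-sorted numerically and printed "to allow quick identification of a particular product code if emergency unblinding is required". No steps are given for the pharmacist's look-up, and the text does not say where the sorted print-out is kept or who reads it.

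The purpose is worded for one person: in an emergency, "an investigator may unblind a subject". The example given is that the "blind would be broken in the event of a serious adverse effect experienced by a subject". The controls are a signed and dated seal, a locked safe in the Neurology offices, and a reporting rule: "Any intentional or unintentional breaking of the blind will be recorded and reported to the sponsor as soon as possible".

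The same section bars investigators and subjects from the randomisation codes and releases the codes to investigators only after database lock.

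**The concern.** The tool discloses more than its purpose needs. Unblinding one subject requires one allocation; the envelope holds all of them. The sequence was generated in advance, so on the natural reading it also covers subjects not yet enrolled. Because Table 1 defines group A as fampridine then placebo and group B as the reverse, one letter gives a subject's treatment in both periods.

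An opening made exactly as the plan directs would therefore conflict with the plan's own bar on investigator access. This is a single-centre trial (section 10.1), so the Principal Investigator's blind would be lost at the only site. The judgements affected are those the protocol leaves to the investigator after that point: relatedness of adverse events (section 12.2.2), and withdrawal of a subject on best-interest grounds (section 10.5, Discontinuation/Withdrawal), for which a reason must be entered on the CRF.

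**Working it through.** **What one opening reveals.** Side by side, the passages answer different questions.

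- When may the blind be broken? When one subject's assignment is essential to that subject's management (section 10.3.3).
- What is then opened? An envelope with the randomisation code and both product-code lists (sections 10.3.3 and 12.2.5).
- What limits the disclosure to that subject? Nothing stated. There are no per-subject envelopes, and no procedure for releasing a single allocation. The sorted list helps to find one code but gives the status of every code.
- What happens to the other subjects' blind afterwards? Nothing stated.

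The seal, the safe and the reporting rule make an opening visible. They do not limit what it shows.

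**How many subjects would be affected, given one opening.** Inputs from the documents: 80 subjects (section 13.2), 22 weeks per subject (section 10.1), and recruitment planned for 6 months with 12 months as the outer limit (section 10.4.1). Assumptions: subjects enter evenly over R weeks, and the break occurs at a random time 2 to 20 weeks after the index subject's screening.

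Another subject has finished by the time of the break only if that subject entered at least d weeks before the index subject, where d = 22 − (weeks from index screening to break). So d is uniform on 2 to 20, and the probability for a given d is (R − d)² / (2R²). Averaging over d, the share still with assessments to come is

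1 − {[(R − 2)³ − (R − 20)³] / (3 × 18)} / (2R²)

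- R = 26: (13,824 − 216)/54 = 252; 252/1,352 = 0.186; share 0.814; × 79 = 64.3.
- R = 52: (125,000 − 32,768)/54 = 1,708; 1,708/5,408 = 0.316; share 0.684; × 79 = 54.0.

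The count includes subjects not yet enrolled. If only the index subject's allocation were disclosed, it would be 0.

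**How likely an opening is.** The documents give no code-break rate. The one related figure is 0.32 first seizures per 100 subject-years (section 8.2).

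- Active weeks only: 80 × 8 / 52.18 = 12.27 subject-years; × 0.0032 = 0.039 expected; chance of at least one about 3.8%.
- If placebo weeks carried a similar rate (an assumption): 2 × 0.039 = 0.079 expected; 7 to 8%.

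Seizure is only one possible trigger. The plan's example is any serious adverse effect, for which no rate is given.

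**Separate check: the product codes.** Section 10.3.3 (Blinding, item 4) states 1,400 numbers from 1,000 to 2,199, split 700 and 700.

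- Size of the range: 2,199 − 1,000 + 1 = 1,200, so the stated 1,400 is not reproduced.
- 1,400 consecutive numbers from 1,000 end at 1,000 + 1,400 − 1 = 2,399.
- Need: 80 subjects × 8 weekly boxes (section 11.2) = 640 boxes per product. With 700 codes there are 60 spare; with 600 there would be 40 too few.

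The count and the split fit the supply need, so the upper limit is probably the typing error.

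**The case against.** The strongest reply is that full disclosure is an inference. The layout of the envelope is not described, and entries could be separately concealed. The sorted print-out is described directly after the unblinding procedure and may be the very list in the envelope, so its location may not be missing. Each box label carries a product code, so a reader could look up one box without consulting the A/B sequence. This stands as a reason for moderate confidence. It does not remove the gap: no text requires such restraint or provides for it, and the randomisation code is in the same envelope.

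A second reply is that openings are rare and controlled. The only figure derivable from the documents is low, and every break must be reported. That also stands, but reporting does not restore a lost blind.

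A reader might go further and infer that an unblinded investigator could shift the primary result by withdrawing subjects, because section 13.9 bases the primary analysis on complete cases despite the intention-to-treat label in section 13.3. The documents do not support a size for this. Withdrawal is tied to the subject's interest and the reason is recorded. Response in both periods is known only after assessment 8, when the paired data already exist. Nor do the documents say that the Principal Investigator runs the timed tests. Advance knowledge of the sequence at enrolment is a weak route, since every subject is planned to receive both treatments. The comparison of all adverse events in section 13.6 does not depend on relatedness.

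A reader might also infer that 200 codes stand for both active and placebo (700 + 700 − 1,200). That would follow only if the printed range is right and the count wrong, which the supply need makes unlikely.

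**Conclusion.** The point holds as a blinding gap that is cheap to close, with moderate confidence. On the natural reading, one authorised opening can unblind the Principal Investigator to the sequence of all current and future subjects, against the protocol's own bar on access. About 54 to 64 of the 79 others would then still have assessments to come. Those counts are conditional on an opening, on the entry and timing assumptions above, and on the whole list being read.

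The overall probability of an opening is unknown: about 4% from seizures in active weeks alone, with a wider trigger in the text. The consequence is loss of blind for later judgements such as relatedness and best-interest withdrawal. No amount of bias in the efficacy result is shown, and none should be quoted.

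The product-code count is a separate minor correction and adds no weight to the blinding point.

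**What to change.** Replace the single envelope with one sealed envelope per subject, showing only that subject's sequence. Sequence and treatment period together identify the assigned treatment, so no product-code list is needed in the envelope. Keep the full randomisation list and both product-code lists, including the numerically sorted print-out, in pharmacy only. Align the wording in section 10.3.3 (security of codes, procedure for unblinding, sorted list) and section 12.2.5. When the blind may be broken is a clinical matter and need not change.

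The cost is preparing about 80 envelopes from the existing list, plus these wording changes. Emergency access for the affected subject is kept, and no patient data are added.

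For the minor point, correct the upper limit (probably to 2,399) or the count against the actual list, and confirm once on the sorted list that no code appears as both active and placebo.

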10.4 DEFINITION OF END-OF-TRIAL

The trial will end on the date of the last visit of the last subject. The Sponsors and/or the trial steering committee have the right at any time to terminate the study for clinical or administrative reasons.

The end of the study will be reported to the REC and Regulatory Authority within 90 days, or 15 days if the study is terminated prematurely. The investigators will inform subjects and ensure that the appropriate follow-up is arranged for all involved. A summary report of the study will be provided to the REC and Regulatory Authority within 1 year of the end of the study.

10.4.1 End of study visits: procedures and assessments:

The end-of-trial is the date of the last visit of the last subject.

The end of study visit form will include:

- assessment 9-HPT, JTT, T25FW, MSIS-29, MSWS-12, DASH, AMSQ, EDSS.
- assessments of safety including general neurological examination and recording of adverse events.
- assessment of compliance with study treatment.
- recording of concomitant medication

Premature termination of the study

Health authorities and ethics committees must be notified of completion or termination of this study, and sent a copy of the study synopsis in accordance with the necessary timelines. This study will be terminated early if recruitment is slow. Recruitment should take 6 months. If recruitment targets are not met and recruitment has slowed to more than 12 months the trial will be terminated.

